3.2 Rationale of study design

This randomized, multi-center, double blind (patient and investigator blind, sponsor open label), placebo-controlled, cross-over study is designed to assess safety, tolerability and efficacy of LJN452 at 60 μ g relative to placebo in patients with pBAD, as assessed by a reduction in stool frequency and stool type score after 2 weeks of double-blind treatment.

A cross-over design reduces variability as the treatment comparison can be done within patient.

Randomization will be maintained at 1:1 ratio over the entire study in order to avoid any sequence bias.

Multiple sites will be used to enroll patient in this study due to the underlying prevalence of diagnosed pBAD. It is known that differences in criteria exist in the diagnosis of pBAD in different regions.

In order to maintain the scientific integrity of the study, investigators and patients will remain blinded regarding the allocation of active or placebo. The clinical trial team will be unblinded throughout the dosing phase to allow analysis of safety and PK/PD data.

3.4 Rationale for choice of comparator

There is no FXR agonist approved drug for treatment of bile acid diarrhea, thus placebo will be used as a comparator in this study.

Corporate Confidential Information

3.6 Risks and benefits

No more than a transient direct benefit of LJN452 treatment to patients with pBAD is anticipated in the short term study.

A maximum of 438 mL of blood is planned to be collected over a period of 8 weeks from each patient as part of the study. Additional samples needed for monitoring of any safety findings would be in addition to this. This is not considered to be a risk for this population.

There may be unknown risks of LJN452 which may be serious and unforeseen.

The overall risk to patients with pBAD in this study is expected to be low and will be minimized by adherence to the inclusion/exclusion criteria, avoidance of prohibited concomitant medications, close clinical monitoring including on-line PK assessments, safety reviews and study stopping rules.

The overall risk/benefit assessment of LJN452 is supportive of the conduct of this study in patients with pBAD.

4 Population

The study population will be comprised of patients with primary bile acid diarrhea.

A total of approximately 30 patients will be enrolled in the study and randomized, with at least 24 patients expected to complete the study.

The investigator must ensure that all patients being considered for the study meet the following eligibility criteria. No additional criteria should be applied by the investigator to ensure that the study population will be representative of all eligible patients.

Patient selection is to be established by checking through all eligibility criteria at screening. A relevant record (e.g. checklist) of the eligibility criteria must be stored with the source documentation at the study site.

Deviation from **any** entry criterion excludes a patient from enrollment into the study.

Replacement patients will be enrolled to replace patients who discontinue the study for reasons other than safety.

4.1 Inclusion criteria

1. Written informed consent must be obtained before any assessment is performed.
2. A history of diarrheal symptoms for at least 3 months prior to dosing
 - Average stool frequency of at least 3 per day when off therapy.

AND

 - Average stool form of >5 on Bristol Stool Chart.
3. Previous laboratory or radiological confirmation within the last 5 years of bile acid malabsorption with either:
 - Evidence of fecal bile acid loss of $\geq 2,000 \mu\text{mol}$ per 48 hours.

OR

 - 7 day ^{75}S elenium homocholic acid taurine ($^{75}\text{SeHCAT}$) retention of <10%.
4. Age ≥ 18 years

6. Able to communicate well with the investigator, to understand and comply with the requirements of the study.

4.2 Exclusion criteria

Corporate Confidential Information

2. Patients with other diagnoses leading to diarrhea, including colorectal neoplasia, ulcerative colitis, Crohn's disease, celiac disease, chronic pancreatitis, drug-induced diarrhea or active infection

AND

Patients who have not been investigated by standard clinical assessments to exclude these disorders.

3. Treatment with bile acid sequestrants (colestyramine, colestipol, colesevelam) for 2 weeks before the first dose of LJN452. A washout of 14 days for these agents will be allowed before first dosing.
4. Use of drugs or agents of the classes within 1 week prior to dosing or planned use during the study period:
 - Agents that alter GI transit except loperamide, including strong opioids, narcotics, anticholinergics.
 - Any medication that could interfere with the interpretation of the study (thyroxine replacement is a permissible exception).
5. History of extrahepatic biliary obstructive disease or complete biliary obstruction.

Corporate Confidential Information

- Evidence of urinary obstruction or difficulty in voiding at screening.

8. Pregnant or nursing (lactating) women, where pregnancy is defined as the state of a female after conception and until the termination of gestation, confirmed by a positive hCG laboratory test.

9. History of malignancy of any organ system (other than localized basal cell carcinoma of the skin or treated cervical intraepithelial neoplasia), treated or untreated, within the past 5 years, regardless of whether there is evidence of local recurrence or metastases.

10. Sexually active males must use a condom during intercourse while taking drug and for 5 days after stopping LJN452 and should not father a child in this period. A condom is required to be used also by vasectomized men in order to prevent delivery of the drug via seminal fluid.

11. Significant mental and physical illness other than pBAD which has not resolved within two (2) weeks prior to initial dosing.

12. Women of child-bearing potential, defined as all women physiologically capable of becoming pregnant, unless they are using highly effective methods of contraception during dosing and for 5 days after stopping of LJN452. Highly effective contraception methods include:

- Total abstinence from heterosexual intercourse (when this is in line with the preferred and usual lifestyle of the subject). Periodic abstinence (e.g. calendar, ovulation, symptothermal, post-ovulation methods) and withdrawal are not acceptable methods of contraception.
- Female sterilization (have had surgical bilateral oophorectomy with or without hysterectomy), total hysterectomy or tubal ligation at least six weeks before taking investigational drug. In case of oophorectomy alone, only when the reproductive status of the woman has been confirmed by follow up hormone level assessment.
- Male sterilization (at least 6 months prior to screening). For female subjects on the study the vasectomized male partner should be the sole partner for that subject.
- Use of oral (estrogen and progesterone), injected or implanted hormonal methods of contraception or placement of an intrauterine device (IUD) or intrauterine system (IUS) or other forms of hormonal contraception that have comparable efficacy (failure rate <1%), for example hormone vaginal ring or transdermal hormone contraception

In case of use of oral contraception, women should be stable on the same pill for a minimum of 3 months before taking investigational drug.

13. A positive Hepatitis B surface antigen or Hepatitis C test result.

14. History of immunodeficiency diseases, including a positive HIV (ELISA and Western blot) test result.

15. No additional exclusions may be applied by the investigator, in order to ensure that the study population will be representative of all eligible patients.

5 **Restrictions for Study Subjects**

During recruitment, screening/informed consent review, and treatment day 1 visit, the patients must be informed and reminded of the restrictions.

5.1 Contraception requirements

Please refer to exclusion criteria ([Section 4](#)) for details of contraception requirements for the study.

5.2 Prohibited treatment

No medication or herbal remedies likely to have an impact on LJN452 metabolism will be allowed from the first dosing until end of study evaluations have been conducted.

Corporate Confidential Information

Administration of acetaminophen (no more than 1000 mg in a single dose and no more than 4000 mg per day) is acceptable, but must be documented.

A full list of prohibited medications will be provided in the SOM.

5.3 Dietary restrictions and smoking

- Patient must avoid high fat foods during the study and adhere to a diet that is similar across both periods of the cross-over design.

All patients will fast (i.e. no food and liquid except water) for at least 8 hours prior to administration of study drug and will continue to fast (i.e. no food and liquid except water) for at least 2 hours thereafter.

Food intake will be monitored regularly throughout the study using a patient diary and will be included in the clinical database.

Patients can drink water *ad libitum* in addition to fluid taken with meals and medication.

On PK days Day 1 and Day 12, no breakfast will be provided. Meals should be similar in caloric content and distribution for all patients on the day of dosing.

5.4 General restrictions

No strenuous physical exercise (e.g. weight training, aerobics, football) until after Study Completion evaluation.

6 Treatment

6.1 Study treatment

Details on the storage and management of study medication, randomization and instructions for prescribing and taking study treatment are outlined in Section 3 of the Site Operations Manual.

6.1.1 Investigational treatment

The investigational drug, LJN452 10 µg (0.01 mg), and matching placebo will be prepared and supplied by Novartis as single blinded packs to be dispensed by the unblinded pharmacist at the investigator site according to the randomization schedule.

6.2 Treatment arms

Patients will be assigned to the 2 treatment sequence (Drug/Placebo or Placebo/Drug) in a ratio of 1:1. The number of patients enrolled may change based on data from interim analyses.

Study treatments are defined as:

- A: Single oral dose of LJN452 60 µg daily for 14 days (administered as LJN452 6 x 10 µg capsules).
- B: Single oral dose of placebo to LJN452 0 µg daily for 14 days (administered as placebo to LJN452 6 x 0 µg capsules).

6.3 Permitted dose adjustments and interruptions of study treatment

Study drug dose adjustments by the investigator and/or interruptions other than for safety reasons are not permitted.

In case of notable adverse events, safety concerns and/or based on pharmacokinetic data review during the study, the following changes to the administered dose may be considered by the sponsor in consultation with the investigator:

- Administration of a dose below the starting dose.
- Administration of a dose higher than the starting dose not exceeding the exposure cap.

These changes must be recorded on the Dosage Administration Record CRF.

6.4 Treatment assignment

Randomization numbers will be assigned in ascending, sequential order to eligible patients (see Site Operations Manual for details). The investigator will enter the randomization number on the CRF.

The randomization numbers will be generated using the following procedure to ensure that treatment assignment is unbiased and concealed from patients and investigator staff. A randomization list will be produced by or under the responsibility of Novartis Drug Supply Management using a validated system that automates the random assignment of treatment arms to randomization numbers in the specified ratio. The randomization scheme for patients will be reviewed and approved by a member of the Novartis IIS Randomization Group.

6.5 Treatment blinding

This is a double blind study: Patients, investigator staff, and persons performing the assessments will remain blinded to the identity of study treatments according to the specifications provided in the Site Operations Manual.

The identity of the treatments will be concealed by the use of study drugs that are all identical in packaging, labeling, schedule of administration, appearance, and odor.

Randomization data are kept strictly confidential until the time of unblinding, and will not be accessible by anyone else involved in the study with the following exceptions: Unblinded pharmacist or authorized designee at site, and the sponsor clinical trial team.

The Interim Analysis Team may communicate interim analysis results (e.g. information needed for planning/modifying another study) to relevant Novartis teams for information, consulting and/or decision purposes.

The sponsor clinical trial team will remain unblinded throughout the study.

Unblinding to the investigator and patient will only occur in the case of patient emergencies (see [Section 6.6](#)) and at the conclusion of the study or after IAs.

6.6 Emergency breaking of assigned treatment code

Emergency unblinding should only be undertaken when it is essential to treat the patient safely and efficaciously. Most often, study treatment discontinuation and knowledge of the possible treatment assignments are sufficient to treat a study patient who presents with an emergency condition. A complete set of emergency code break cards will be provided to the investigator site(s) and a complete set will be available at Novartis. All code break cards must be retained until the end of the study and returned to Novartis. They must be stored in a secure place but be accessible in case of emergency. The investigator will receive a blinded code break card for each patient, with the details of drug treatment covered by a removable, scratch-off cover. In an emergency, the scratch-off cover can be removed to determine the treatment. The scratch-off covers are not to be removed for any reason other than an emergency. When the investigator removes the scratch-off cover he/she must note the date, time, and reason for removing it and retain this information with the case report form documentation. **The unblinded treatment code should not be recorded on the CRF.** The investigator must also immediately inform the Novartis local monitor that the code has been broken.

6.7 Treatment exposure and compliance

Pharmacokinetic parameters (measures of treatment exposure) will be determined in all patients treated with LJN452, as detailed in [Section 8.5](#).

6.8 Recommended treatment of adverse events

Expression of ALP is induced by FXR activation. Hence LJN452 is expected to increase circulating levels of ALP in a dose dependent manner and this will not necessarily indicate liver injury. Elevation of ALP should be interpreted in light of other tests, such as ALT, AST, and total bilirubin levels. Please see specific stopping rules and response to abnormal lever enzyme tests.

Medication used to treat adverse events must be recorded on the Concomitant medications/Significant non-drug therapies CRF.

6.9 Rescue medication

Use of rescue medication (loperamide) will be allowed and must be recorded on the patient diary/Concomitant medications/Significant non-drug therapies CRF after start of study drug.

Rescue medication will be loperamide only and patients will be instructed to take 2 mg dose only after passage of 3 stools of Bristol Stool Scale Type 6 (fluffy pieces with ragged edges, a mushy stool) or Type 7 (watery, no solid pieces, entirely liquid). This dose may be repeated only after 4 hours have elapsed or passage of 4 further stools of Type 6 or 7 (whichever occurs first). A total of no more than 16 mg of loperamide may be taken in a 24 hour period. No BA sequestrants should be used by the patients during this study.

6.10 Concomitant treatment

All prescription medications, over-the-counter drugs and significant non-drug therapies (including physical therapy and blood transfusions) administered or taken within the timeframe defined in the entry criteria prior to the start of the study and during the study, must be recorded on the Concomitant medications/ Significant non-drug therapies section of the CRF.

Medication entries should be specific to trade name, the single dose and unit, the frequency and route of administration, the start and discontinuation date and the reason for therapy.

7 Discontinuation and study completion

7.1 Discontinuation of study treatment

Patients may voluntarily discontinue study treatment for any reason at any time.

Discontinuation of study treatment will be at the discretion of the Investigator, under the following circumstances:

- Any protocol deviation that results in a significant risk to the patient's safety.
- If continuation in the study is deemed detrimental to the patient's well-being.

The appropriate personnel from the site and Novartis will assess whether study treatment should be discontinued for any patient whose treatment code has been broken inadvertently for any reason.

Individual patient withdrawal

Patients may voluntarily discontinue study treatment for any reason at any time.

Study treatment must be discontinued and the patient withdrawn from the study if the patient withdraws consent.

The study treatment must be discontinued and the patient's withdrawal from the study should be at the investigator's discretion if the following occur:

- Pregnancy.
- Intolerable or clinically significant diarrhea.
- Hypersensitivity reaction to LJN452.

- An increase in aminotransferase enzymes (ALT or AST) of greater than 3 x ULN AND EITHER symptoms such as anorexia, fatigue, right upper quadrant abdominal pain or tenderness, fever, rash and/or eosinophilia OR elevation of serum TBL to greater than 2 x ULN OR INR>1.5.
- Medically significant (>8 x ULN) ALT or AST elevation.
- An AE with a CTCAE rating of Grade 3 or higher regardless of drug causality, unless it is caused by elevation of ALT (as above) or an accident that could not reasonably be attributable to the drug.
- An AE with a CTCAE rating of Grade 2 or higher considered to be due to study drug, unless it is caused by elevation of ALT (as above).
- An elevation of ALP or GGT of >2.5 x ULN considered to be due to study drug or >5 × ULN regardless of drug causality.

Patients who discontinue study treatment or who decide they do not wish to participate in the study further should NOT be considered withdrawn from the study UNLESS they withdraw their consent (see [Section 7.3](#)). Where possible, they should return for follow up assessments. If they fail to return for assessments for unknown reasons, every effort (e.g. telephone, e-mail, letter) should be made to contact them as specified in [Section 7.2.1](#).

7.2 Study completion and post-study treatment

Each patient will be required to complete the study in its entirety and thereafter no further study treatment will be made available to them. Study completion is defined as when the last patient completes their End of Study visit, and any repeat assessments associated with this visit have been documented and followed-up appropriately by the Investigator, or in the event of an early study termination decision, the date of that decision.

At a minimum, patients will be contacted for safety evaluations during the 30 days following the Study Completion visit, including a final post-study safety contact at the 30-day point. Documentation of attempts to contact the patient should be recorded in the source documentation.

The investigator must provide follow-up medical care for all patients who are prematurely withdrawn from the study, or must refer them for appropriate ongoing care. All patients who complete the study will return to their standard of care after the end of study visit.

7.2.1 Lost to follow-up

For patients whose status is unclear because they fail to appear for study visits without stating an intention to discontinue or withdraw, the investigator should show "due diligence" by documenting in the source documents steps taken to contact the patient, e.g. dates of telephone calls, registered letters, etc. A patient should not be formally considered lost to follow-up until his/her scheduled end of study visit would have occurred.

7.3 Withdrawal of consent

Patients may voluntarily withdraw consent to participate in the study for any reason at any time.

Withdrawal of consent occurs only when a patient does not want to participate in the study anymore **and** does not want any further visits or assessments **and** does not want any further study related contact **and** does not allow analysis of already obtained biologic material.

If a patient withdraws consent, the investigator must make every effort to determine the primary reason for this decision and record this information. Study treatment must be discontinued and no further assessments conducted. All biological material that has not been analyzed at the time of withdrawal must not be used. Further attempts to contact the patient are not allowed unless safety findings require communicating or follow-up.

7.4 Study Stopping rules

The study will be placed on hold and may be stopped or amended based on full review of all available clinical safety data and discussion with the Investigator if any of the following occur:

- Two or more patients on study drug experience a similar adverse event that is a CTCAE Grade 3 or higher apart from ALT elevation (see below).
- One patient on study drug experiences any adverse event that is CTCAE Grade 4 or higher apart from ALT elevation (see below) other than an accident that is not related to study drug).
- Two or more patients with an increase in aminotransferase enzymes (ALT or AST) of greater than 3 x ULN AND EITHER symptoms such as anorexia, fatigue, right upper quadrant abdominal pain or tenderness, fever, rash and/or eosinophilia OR elevation of serum total bilirubin to greater than 2 x ULN OR INR >1.5.
- Two or more patients on study drug experience an elevation of ALP or GGT of >5 × ULN or one patient on study drug experiences an elevation of ALP or GGT of >20 × ULN.
- The Principal Investigator and the Sponsor consider that the number and/or severity of adverse events justify discontinuation of the study.
- The Sponsor unilaterally requests discontinuation of the study.

Safety reviews will be conducted jointly between medically qualified representatives of the Sponsor and Investigator and a joint decision will be made. The severity of adverse events will be graded by the study site Investigator (or his designee) based on clinical judgment and captured in the CRF AE page. This information will be used to quantify events that may lead to patient's discontinuation or stopping of the study.

Patients may voluntarily withdraw from the study for any reason at any time. They may be considered withdrawn if they state an intention to withdraw, fail to return for visits, or become lost to follow-up for any other reason. If a patient withdrawal occurs for any reason, the Investigator must make every effort to determine the primary reason for a patient's withdrawal from the study and record this information on the Study Completion CRF.

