Liver events	ALT or AST > 5 × ULN ALP > 2 × ULN (in the absence of known bone pathology) TBL > 2 × ULN (in the absence of known Gilbert syndrome) ALT or AST > 3 × ULN and INR > 1.5 Potential Hy's Law cases (defined as ALT or AST > 3 × ULN and TBL > 2 × ULN [mainly conjugated fraction] without notable increase in ALP to > 2 × ULN) Any clinical event of jaundice (or equivalent term) ALT or AST > 3 × ULN accompanied by (general) malaise, fatigue, abdominal pain, nausea, or vomiting, or rash with eosinophilia Any adverse event potentially indicative of a liver toxicity *

Table 9-2 Follow Up Requirements for Liver Events and Laboratory Triggers

Criteria	Actions required	Follow-up monitoring
Potential Hy's Law case ^a	
 • Discontinue the study drug immediately • Hospitalize, if clinically appropriate • Establish causality • Complete liver CRF 	ALT, AST, TBL, Alb, PT/INR, ALP and GGT until resolution ^c (frequency at investigator discretion)
ALT or AST		
> 8 × ULN	
 • Discontinue the study drug immediately • Hospitalize if clinically appropriate • Establish causality • Complete liver CRF 	ALT, AST, TBL, Alb, PT/INR, ALP and GGT until resolution ^c (frequency at investigator discretion)
> 3 × ULN and INR > 1.5	
 • Discontinue the study drug immediately • Hospitalize, if clinically appropriate • Establish causality • Complete liver CRF 	ALT, AST, TBL, Alb, PT/INR, ALP and GGT until resolution ^c (frequency at investigator discretion)
> 5 to ≤ 8 × ULN	
 • Repeat LFT within 48 hours • If elevation persists, continue follow-up monitoring • If elevation persists for more than 2 weeks, discontinue the study drug • Establish causality • Complete liver CRF 	ALT, AST, TBL, Alb, PT/INR, ALP and GGT until resolution ^c (frequency at investigator discretion)
> 3 × ULN accompanied by symptoms ^b	
 • Discontinue the study drug immediately • Hospitalize if clinically appropriate • Establish causality • Complete liver CRF 	ALT, AST, TBL, Alb, PT/INR, ALP and GGT until resolution ^c (frequency at investigator discretion)
> 3 to ≤ 5 × ULN (patient is asymptomatic)	
 • Repeat LFT within the next week • If elevation is confirmed, initiate close observation of the patient 	Investigator discretion Monitor LFT within 1 to 4 weeks
ALP (isolated)		

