9.5 Early phase safety monitoring

The Investigator will monitor adverse events in an ongoing manner and inform the Sponsor of any clinically relevant observations. Any required safety reviews will be made jointly between medically qualified personnel representing the Sponsor and Investigator. Such evaluations may occur verbally, but the outcome and key discussion points will be summarized in writing (e-mail) and made available to both Sponsor and all Investigator(s). Criteria pertaining to stopping the study/treatment or adapting the study design are presented above.

When two or more clinical site(s) are participating in the clinical study, the Sponsor will advise the Investigator(s) at all sites in writing (e-mail) (and by telephone if possible) of any new, clinically relevant safety information reported from another site during the conduct of the study in a timely manner.

10 Data review and database management

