10.4 Data Monitoring Committee

A Data Monitoring Committee (DMC) has been assembled for this compound to monitor safety data. This committee is comprised of Novartis personnel not directly involved with the study and include one or more Novartis physician with expertise in the indication. The DMC will convene as outlined in the DMC Charter to review an event or combination of events that fulfil the study stopping rules defined in [Section 7.4](#).

In addition, adverse events, including clinical laboratory data will be continuously reviewed by the Novartis Clinical trial team, including the study physician, on an ongoing basis as data become available from the Electronic Data Capture system.

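### Section 7.4 takes ALT elevation out of its Grade 3 and Grade 4 study holds, but no numeric hold covers an isolated ALT rise; the matching ALT-only exemptions in 7.1 leave AST >5 to ≤8 × ULN out of step with Table 9-2

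*Protocol*

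**What the plan says.** Here an isolated rise means one without symptoms, without TBL >2 × ULN and without INR >1.5.

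**Study hold (Protocol 7.4).** There are six items, of which the first four are numeric.

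1. At least two patients receiving study drug "experience a similar adverse event that is a CTCAE Grade 3 or higher apart from ALT elevation (see below").
2. One patient on study drug who "experiences any adverse event that is CTCAE Grade 4 or higher apart from ALT elevation (see below"), apart from unrelated accidents.
3. "Two or more patients with an increase in aminotransferase enzymes (ALT or AST) of greater than 3 x ULN AND EITHER symptoms", or TBL >2 × ULN, or INR >1.5.
4. ALP or GGT >5 × ULN in two or more patients, or >20 × ULN in one.
5. The Principal Investigator and the Sponsor "consider that the number and/or severity of adverse events justify discontinuation of the study".
6. The Sponsor asks for discontinuation.

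Section 10.4 says that the DMC convenes, as its charter sets out, to "review an event or combination of events that fulfil the study stopping rules defined in" Section 7.4.

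**Individual stop (Protocol 7.1).** Discontinuation is mandatory for ALT or AST >3 × ULN with symptoms, TBL >2 × ULN or INR >1.5, and for ALT or AST >8 × ULN alone. It is also mandatory for an AE of Grade 3 or higher from any cause, and for one of Grade 2 or higher due to study drug. Both AE-grade rules exempt ALT elevation by pointing to the items above. Neither names AST.

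**Liver follow-up (Protocol 9.3, Table 9-2).** For ALT or AST >5 to ≤8 × ULN, tests are repeated within 48 hours and monitoring continues. Then: "If elevation persists for more than 2 weeks, discontinue the study drug". The Assessment Schedule footnotes end dosing on Day 14 of each period and set a washout of 7 to 28 days.

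**The concern.** An exemption that points to a rule below should lead to a rule covering what was exempted. In 7.4 it does not: the item below covers ALT only with a second finding. The neighbouring items make the gap visible. ALP and GGT have stand-alone holds in 7.4, 7.1 has a stand-alone >8 × ULN item, and every liver item in 7.1, 7.4 and Table 9-2 that sets an aminotransferase threshold names ALT or AST together. Only the exemptions single out ALT.

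Safety and tolerability is a primary objective, and Section 3.6 lists the study stopping rules among the measures that keep risk low. Followed literally, a cluster of isolated high ALT triggers no numeric hold. On the protocol's text it would then reach the DMC only through items 5 or 6. For AST in the >5 to ≤8 × ULN band, a site may find a mandatory stop in one section and a conditional, later stop in another.

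**Working it through.** No plan figure is available to reproduce. The check compares the rules and then counts days.

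**Step 1. Isolated rises against the four numeric holds in 7.4.**

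| Item | Isolated ALT | Isolated AST |
|---|---|---|
| 1. Grade 3+, two patients | exempt | open, if recorded as an AE of that grade |
| 2. Grade 4+, one patient | exempt | open, if recorded as an AE of that grade |
| 3. >3 × ULN plus second finding | not met | not met |
| 4. ALP/GGT | not relevant | not relevant |
| Numeric items that can be met | 0 of 4 | 2 of 4 |

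The ALT column does not change with height or with the number of patients. Any number of the approximately 30 patients with isolated ALT >8 × ULN meets 0 of 4, although each would be stopped individually under 7.1 and Table 9-2.

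**Step 2. The same isolated values against 7.1 and Table 9-2.**

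| Value | 7.1 liver items | 7.1 AE-grade rules | Table 9-2 |
|---|---|---|---|
| ALT >5 to ≤8 × ULN | none | exempt | stop if it persists >2 weeks |
| AST >5 to ≤8 × ULN | none | stop, if an AE of the stated grade | stop if it persists >2 weeks |
| ALT or AST >8 × ULN | stop | – | stop immediately |

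Section 9.1 treats a laboratory value as an AE only if it causes signs or symptoms, is clinically significant or needs therapy. It cites CTCAE version 4, but neither document gives the cut-offs. The AST entry is therefore conditional on recording and grade.

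**Step 3. When the persistence clause can be met.** Let d be the onset day within a course, 1 to 14, with the last dose on Day 14. The clause is first met on:

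- Day d + 14, if onset counts as day 1: Day 15 (d = 1) to Day 28 (d = 14).
- Day d + 15, in elapsed days: Day 16 to Day 29.

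Both ranges start after Day 14, so 0 of 14 onset days meet the clause during the course in which the rise begins.

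With washout w, period 2 dosing runs from study day 15 + w to 28 + w. That is days 22–35 for w = 7 and days 43–56 for w = 28. For a rise that begins in period 1:

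- w = 7: onset on Days 8–14 (or 7–14 in elapsed days) meets the clause during period 2 dosing. Earlier onsets meet it before period 2.
- w = 28: the latest clause day is 28 (or 29), before day 43, so every onset meets it before period 2.

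A rise that begins in washout can also reach the clause in period 2. A rise that begins in period 2 reaches it only after dosing has ended. Onset is used rather than detection because the body of the Assessment Schedule is not shown; later detection only moves these days later.

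**The case against.** **Judgement covers the gap.** This largely stands. Item 5 of 7.4 addresses the number and severity of adverse events. Section 9.5 adds that "Any required safety reviews will be made jointly between medically qualified personnel representing the Sponsor and Investigator". Section 10.4 provides continuous review by the trial team, and under 6.5 "The sponsor clinical trial team will remain unblinded throughout the study". A reader might infer that isolated ALT goes unwatched or can never reach the DMC. The documents do not support that: items 5 and 6 are themselves 7.4 rules, so the DMC can be reached through them, and its charter is not available. What is missing is a numeric criterion where the text points to one.

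**The exemption may be narrower than it looks.** One could read it as removing only those ALT rises that item 3 covers, leaving isolated ALT under items 1 and 2. That reading is implausible. One isolated Grade 4 ALT would hold the study, while one case of the worse composite picture would be exempt and would need a second patient. The plain reading is the sensible one.

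**The exemption may be deliberate.** It may be. The visible text gives no reason for it or for the ALT/AST difference, though parts of the protocol are redacted.

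**The AST passages do not flatly contradict each other.** This stands in part. A reader might infer a direct clash, but Table 9-2 does not forbid earlier stopping, and 9.3 refers discontinuation to 7.1 where appropriate. The mismatch arises only if the value is recorded as an AE of the stated grade. For ALT in this band, 7.1 is silent rather than contradictory.

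**The 2-week clause still works.** A reader might infer that it is void. It is not, because it can prevent or stop period 2 dosing. Discontinuation for well-being (7.1) and interruption for safety (6.3) also remain available throughout.

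**Conclusion.** The point holds as a mismatch between written rules. The firm part is in 7.4: isolated ALT at any height meets 0 of 4 numeric holds, against 2 of 4 for isolated AST recorded at the stated grade, and the pointer in the exemption leads to no isolated-ALT criterion. The AST difference between 7.1 and Table 9-2 is conditional on AE recording and grade. The timing result, 0 of 14 onset days within the same course, holds under both ways of counting days. It concerns only rises that begin during that course.

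These are counts of rules and calendar days, not event rates, and they say nothing about how often such rises would occur. They do not show an absence of safety oversight or that any particular rule is clinically wrong. The point merits consideration and no higher rating.

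**What to change.** Reconcile the ALT-only exemptions in 7.4 and 7.1, and the references they carry to items below or above, with the liver items that name ALT or AST. State whether the ALT/AST difference is intended and whether isolated ALT is meant to be left to items 5 and 6 of 7.4. Reconcile the Table 9-2 persistence clause with 7.1 and the 14-day periods: say whether it carries across periods, and how it stands against the AE-grade rules for AST. The content is for the sponsor's safety physicians; no threshold, time window or clinical rule is proposed here.

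The cost is a written protocol amendment, which under Section 13.1 needs sponsor and IRB/IEC approval and Health Authority approval where required. The reconciliation itself needs no new assessment.
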